7.3 Concomitant Medications and Therapies

Medications specifically prohibited in the exclusion criteria are not allowed during the active treatment period. Concomitant treatment considered necessary for the patient's well-being may be given at the discretion of the treating Investigator.

7.3.1 Allowed Therapy

All supportive measures consistent with optimal patient care may be given throughout the study. Patients should receive appropriate supportive care measures as deemed necessary by the treating Investigator.

Version Date: 11APR2023

7.3.2 Prohibited Therapy

Medications or vaccinations specifically prohibited in the exclusion criteria are not allowed during the active treatment period. Patients are prohibited from receiving the following therapies during the treatment phase of this trial:

- Investigational agents, other than those utilized during study therapy.
- Radiation therapy other than the brachytherapy conducted in conjunction with this study.
- Herbal remedies, other than Q-Urol, defined as any substance derived from a botanical source, not prescribed by the physician that a patient is using without professional medical guidance with the intent of treating prostate specific conditions.
- Cyclosporine
- Digoxin
- Warfarin
- CYP2C8 substrates (e.g., repaglinide, paclitaxel, omeprazole, cisapride)

7.3.3 Allowed therapies to be used with caution and the discretion of the treating physician

- While on study therapy, the use of anticoagulants should be used with caution.
- Quercetin may have additive hypoglycemic effects when used with antidiabetic medications; use the combination with caution.
- Quercetin may have varying effects on CYP3A4; substrates of CYP3A4 with a narrow therapeutic index should be used with caution (Appendix 12)
- Quercetin may have additional blood pressure lowering effects when used with anti-hypertensive medications; use the combination with caution
- Quercetin may have inhibitory effects on CYP2C9, CYP2D6, OATP1B1, and P-gp; substrates of these with narrow therapeutic indexes should be used with caution (Appendix 12).

7.4 **Duration of Therapy**

Each patient will be on study therapy for six weeks starting with the day of brachytherapy.

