2.2 Rationale for Q-Urol

Q-Urol is a commercially available supplement whose key active ingredient is Quercetin.

Quercetin has been shown to have the following biological properties:

- A potent free radical scavenger² and antioxidant.³
- An anti-inflammatory agent, which reduces inflammation by inhibiting interleukin-6, interleukin 8, tumor necrosis factor, and NF-κB. 4-7
- In animal models of inflammatory pain, quercetin reduced pain, oxidative stress, and cytokine production.⁸
- Patients with chronic prostatitis who report improvement with quercetin have a reduction in the oxidative stress metabolite F2-isoprostane in their expressed prostatic secretions (EPS). ⁹
- Quercetin therapy reduces inflammation as measured by prostaglandin E2 levels in EPS, and increases the levels of prostatic β -endorphins.¹⁰
- Side effects with quercetin therapy are rare. 11

We propose that the use of Q-Urol will be an effective therapy at reducing symptom burden and distress following prostate brachytherapy procedures due to radiation-induced prostatitis versus a comparator cohort receiving placebo without adding additional toxicity.

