Patients currently undergoing radiation therapies for prostate cancer at the Huntsman Cancer Institute at the University of Utah are not currently counselled to stop antioxidants or supplements, but asked about supplementation use. There is also no recommendation by the NCCN or any other prostate cancer treatment guideline that suggests antioxidants, phytochemicals, minerals or other supplements should be discontinued. Given the

Version Date: 11APR2023

overwhelming amount of evidence from the randomized controlled trials in the contemporary Yasueda meta-analysis, and the current care standard of allowing antioxidant therapies during prostate cancer radiation therapy, the use of antioxidants and phytochemicals used in this study is considered safe by the best evidence available.

2.5 Rationale of definition of ½ standard deviation of the mean for clinically significant difference on the Patient-Reported Outcomes Measures:

A ½ standard deviation from the mean at the baseline for each PRO-QOL measure or domain was specified as the minimal clinically important difference (MID), to be consistent with established convention and other PCa PRO-QOL outcome studies. ¹³⁻¹⁷ Specifically, a ½ standard deviation was defined as the MID on the landmark ProtecT randomized trial which randomized approximately 1800 men to radiation therapy, versus surgery, versus active surveillance using the same PRO forms (EPIC) used in this study. Utilizing this convention will allow the investigators to compare their outcomes not only against the cohorts in this study, but to historical cohorts such as those in ProtecT, as well as studies funded by the Patient-Centered Outcomes Research Institute (PCORI) evaluating QOL in prostate cancer patients receiving radiation therapy. ^{18, 19}

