4 STUDY DESIGN

4.1 Description

This is a Phase 2, double-blinded, placebo-controlled trial assessing the safety of Q-Urol use after brachytherapy placement in patients with localized prostate cancer. Patients will be randomized in a 1:1 ratio to receive Q-Urol/Placebo twice daily for six weeks after brachytherapy placement. Questionnaires will be administered pre- and post-treatment to assess the change in prostatitis symptoms and quality of life measures. The mean values between groups will be compared.

Once 42 patients (21 to each arm) have been enrolled and treated on the study therapy, enrollment will be placed on hold and an interim analysis conducted. The interim analysis will be conducted for futility and efficacy and will be reviewed by the DSMC. If the analysis is favorable, as defined in the Statistical Analysis section, the trial will open to the enrollment of 98 additional subjects, 49 per arm. However, if the analysis does not demonstrate standards defined in the statistical analysis, the trial will be closed to accrual.

Version Date: 11APR2023

Safety monitoring will be overseen by the DSMC at HCI. See Section 12.4 for safety monitoring plan and early stopping rules.

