4.3 Number of Patients

The trial will enroll up to 70 patients to each arm, 140 patients total.

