5.2 Exclusion Criteria

Yes/No (Response of "yes" = patient ineligible) 5.2.1 Baseline AUA symptom scores > 15. 5.2.2 Prior diagnosis of chronic prostatitis type II through IV. Subject has received systemic therapy intended for the treatment of 5.2.3 prostatitis (including herbal supplements) ≤ 14 days of starting study treatment. 5.2.4 Subject has received a fluoroquinolone antibiotic (e.g. ciprofloxacin, norfloxacin, ofloxacin levofloxacin, etc.) ≤ 3 days of starting study treatment. 5.2.5 Subject is actively on anti-inflammatory medications for other medical conditions, unless approved by PI. Subject has undergone transurethral resection of the prostate (TURP). 5.2.6 5.2.7 Patients with a prior or concurrent malignancy whose natural history or treatment has the potential to interfere with the safety or efficacy assessment of the investigational regimen. History of irritable bowel syndrome, chronic fatigue syndrome, 5.2.8 fibromyalgia, and interstitial cystitis-bladder pain syndrome (IC/BPS). 5.2.9 History of symptomatic hypotension, falls, or syncope **5.2.10** Chronic hypoglycemia requiring hospitalization. **5.2.11** Actively abusing alcohol or drugs The subject has uncontrolled, significant intercurrent, or recent illness including, but not limited to, the following conditions: • Congestive heart failure Diabetes Pulmonary artery hypertension Any clinically significant condition that requires therapy with diuretic medications for any indication other than the management of hypertension. Other clinically significant disorders that would, in the opinion of the

treating investigator, preclude safe study participation.

Short Title: Q-Urol								
Version Date: 11API	R2023							
5.2.13	Known prior severe hyper component in its formulations (N	•	C 1	duct or any				
5.2.14	Known allergy to pineapp	le or pineap	ple containing produc	cts.				
5.2.15	washout period of prohibited me	Subjects taking prohibited medications as described in Section 7.3 A shout period of prohibited medications for a period of at least 5 half-lives or clinically indicated should occur prior to the start of treatment.						
I certify that thi study.	s patient meets all inclusion and	d exclusion	criteria for enrollm	ent onto this				
Investigator Sign	nature	Date	 Time					

Version Date: 11APR2023

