13.2 Statistical Analyses

13.2.1 Sample size determination

The outcome for sample size determination is the primary endpoint variable, the peak of the National Institutes of Health-Chronic Prostatitis Symptom Index (NIH-CPSI) total score measured from baseline to six weeks post brachytherapy. The primary hypothesis is that the mean of the primary outcome variable will be $\frac{1}{2}$ standard deviation lower in patients taking Q-Urol compared to placebo. A single interim analysis is planned after N1= 21 subjects per group have outcome data. The interim and final analysis will compare the treatment and control means using nominal t statistics (control minus treatment). If the t statistic has a value less than -1.16 at the interim analysis the trial will be terminated for futility. If the t statistic has a value greater than 2.85 at the interim analysis the trial will be terminated for efficacy.

If the study is not terminated for efficacy or futility at the interim analysis an additional N2 = 49 patients per group will be accrued for a total of N = 70 patients per group. If the interim analysis is done at the planned sample size (21 patients per group) the treatment will be deemed efficacious at the final analysis if the t statistic has a nominal value greater than 1.67.

The above design was evaluated using 100,000 simulated data sets for both the null and alternative hypotheses. There is 90% power at overall one-sided Type I error equal to 0.05 (one-sided) to detect a 0.5 standard deviation lower mean of the primary endpoint in the treatment group compared to the control group. The probability of early termination for futility under the null hypothesis is 12%. The probability of early termination for futility under the alternative hypothesis is 0.3%. The probability of early termination for efficacy under the alternative hypothesis is 12%.

If the interim analysis or final analysis is performed at a sample size that is different than the planned sample size the final analysis will be adjusted to maintain an overall Type I error of no more than 0.05 (one-sided).

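### Supplement restrictions turn on intent and guidance, not ingredient, so placebo patients may take the active ingredients without a deviation

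*Combined protocol and SAP*

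**What the plan says.** Two rules deal with supplements.

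- **Before entry.** Exclusion 5.2.3, repeated in the Study Summary, removes a man who has had systemic treatment aimed at "prostatitis (including herbal supplements) ≤ 14 days of starting study treatment".
- **On study.** Section 7.3.2 prohibits herbal remedies apart from Q-Urol, defined as botanical substances "not prescribed by the physician that a patient is using without professional medical guidance with the intent of treating prostate specific conditions". All the conditions must hold for the ban to apply.

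Section 7.3 carries the exclusion criteria into the treatment period. Exclusion 5.2.15 excludes men taking agents prohibited under Section 7.3 and calls for a washout of at least five half-lives, or as clinically indicated. Exclusion 5.2.5 covers anti-inflammatory medications taken for other conditions, unless the PI approves.

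Section 3.1 lists the product's ingredients as quercetin, pollen extract, bromelain and papain. None is prohibited by name in Section 5.2, Section 7.3 or Appendix 12; Section 7.3.3 mentions quercetin only for its drug interactions. Section 2.2 states that "Q-Urol is a commercially available supplement whose key active ingredient is Quercetin". Section 2.4 says that the site's radiotherapy patients "are not currently counselled to stop antioxidants or supplements, but asked about supplementation use".

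**The concern.** The trial tests four ingredients against placebo, but its rules control why a man takes them and not whether he takes them. A man using bromelain for sinus symptoms (a use described in Section 3.1.1), or quercetin for general health, is caught by neither supplement rule. Nor is a man whose clinician recommends pollen extract for benign enlargement, another use described there. Read literally, the exception for Q-Urol in the herbal item also covers Q-Urol bought in a shop, because it is not limited to study-supplied capsules.

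If placebo patients receive some of the active treatment, the NIH-CPSI difference shrinks and a real effect is more easily missed. The inflammatory markers are exposed in the same way. Because the use is permitted, no deviation is triggered. Section 13.2 has no plan for it, and the baseline characteristics in Section 11.2 and Appendix 9 do not ask about supplements.

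**Working it through.** **1. Which users the rules catch**

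| Use of an active ingredient | Caught? |
|---|---|
| Any treatment aimed at prostatitis | Yes: 5.2.3 at entry, carried into treatment by 7.3 |
| Unprescribed, unguided, for another prostate condition | Yes: 7.3.2, and 5.2.15 at entry |
| Prescribed or guided, for another prostate condition | No |
| Non-prostate reason, taken as an anti-inflammatory | Arguably, under 5.2.5, unless the PI approves |
| Non-prostate reason, otherwise | No |

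The shop-bought Q-Urol exception lies within the herbal item of 7.3.2. It does not lift the separate bar on treatment aimed at prostatitis.

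**2. Inputs for the size of the effect**

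- Section 13.2.1: power 90%, one-sided type I error 0.05, target effect 0.5 SD in favour of Q-Urol.
- Section 4.3: "The trial will enroll up to 70 patients to each arm, 140 patients total". Section 4.1 gives 1:1 allocation.
- Section 13.2.1 rules: interim at 21 per arm, futility if t < -1.16, efficacy if t > 2.85; final analysis at 70 per arm, success if t > 1.67.
- Assumed, because the documents give no figure: the share *c* of placebo patients using an active ingredient, and the fraction *r* of the Q-Urol benefit that they obtain.

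**3. The plan's own figures reproduce.** Simulating the stated design (200,000 trials under the alternative, 400,000 under the null):

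| Quantity | Plan | Simulated |
|---|---|---|
| Power at 0.5 SD | 90% | 89.9% |
| One-sided type I error | 0.05 | 0.0502 |
| Futility stop, null | 12% | 12.6% |
| Futility stop, alternative | 0.3% | 0.28% |
| Efficacy stop, alternative | 12% | 12.4% |

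The fixed-sample formula agrees: Φ(0.5 × √(70/2) − 1.645) = Φ(2.958 − 1.645) = Φ(1.313) = 90.5%.

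**4. Placebo-arm use, with no added benefit from extra use in the Q-Urol arm.** The contrast becomes 0.5 × (1 − *c* × *r*) SD. For example, *c* = 10% and *r* = 1 gives 0.5 × 0.90 = 0.45 SD. The last column is the fixed-design size for 90% power, against 69 with no such use.

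| *c* | *r* | Contrast (SD) | Simulated power | n per arm for 90% |
|---|---|---|---|---|
| 0 | – | 0.500 | 89.9% | 69 |
| 5% | 1 | 0.475 | 87.0% | 76 |
| 10% | 1 | 0.450 | 83.7% | 85 |
| 20% | 1 | 0.400 | 75.1% | 108 |
| 5% | 0.5 | 0.4875 | 88.7% | 73 |
| 10% | 0.5 | 0.475 | 87.3% | 76 |
| 20% | 0.5 | 0.450 | 83.7% | 85 |

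**5. Additive benefit, equal use in both arms.** The mean difference stays at 0.5 SD and only the variance grows. At *c* = 20% and *r* = 1 the variance is 1 + 0.2 × 0.8 × 0.5² = 1.04, so the SD is 1.02 and the standardised contrast is 0.5/1.02 = 0.490. Power is Φ(0.490 × 5.916 − 1.645) = Φ(1.26), about 89.5%, against 90.5% on the same fixed-sample basis. The loss is about 1 point.

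**The case against.** Much of the case on the other side stands.

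- **The most predictable contamination is already barred.** A symptomatic man who takes Q-Urol on his own initiative for prostatitis falls under 5.2.3 as carried forward by Section 7.3. A reader might infer from the Q-Urol exception that he is free to do so; the documents do not support that.
- **There is a washout.** A reader might infer that a man taking pollen extract unguided for benign enlargement enters with none, because 5.2.3 does not reach him. Exclusion 5.2.15 does, through Section 7.3. It does not help with uses that Section 7.3 never prohibits.
- **Use in the Q-Urol arm does not shrink the contrast.** A reader might infer dilution from both arms. Extra quercetin there either widens the difference or, if the effect is saturated, leaves it unchanged.
- **Full benefit is an upper bound.** Section 3.1.1 itself says that research on bromelain and papain is limited, so a man taking one of these need not obtain the effect of the whole product.
- **5.2.5 may catch some users.** The protocol calls its own capsules medication and describes quercetin as anti-inflammatory, so the criterion can be read to include such supplements. But it does not name them, as 5.2.3 does, and it can be waived.
- **Use may be captured.** The weekly calls collect concomitant medications. They do not specify supplements.

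The instruction in Section 7.2.2 not to take extra medication sits among the study-capsule dosing instructions and is not a clear ban on other products. Section 2.4 describes clinic practice and is not a trial rule. After all this, the wording gap remains; it is the size of its effect that is uncertain.

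**Conclusion.** The wording gap is real. The restrictions depend on intent and guidance, and a placebo patient can take the tested ingredients without breaching them. The bias runs toward no effect, and the plan's type I error and power calculations are otherwise sound.

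The size is unknown. The loss ranges from about 1 point of power (equal use, additive benefit, or 5% placebo use at half benefit) to about 15 points (20% placebo use at full benefit). It becomes material from roughly 10% placebo use at full benefit. These figures rest on assumed shares and assumed relative benefit, and those in step 4 also assume that extra use adds nothing in the Q-Urol arm. They should not be read as a forecast of the power that the trial will lose. Confidence is high on the wording and low on the magnitude.

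**What to change.** 1. In 5.2.3, the Study Summary and Section 7.3.2, define the supplement restriction by ingredient: any non-dietary product containing quercetin, bromelain, papain or flower-pollen extract, whatever the reason for use and with or without professional guidance, up to completion of the end-of-treatment questionnaires.
2. State that the Q-Urol exception in 7.3.2 means study-supplied product only.
3. Ask about these products by name at screening and at the existing weekly calls, so that use can be tabulated by arm.
4. Reconcile the 14-day period in 5.2.3 with the five-half-life washout in 5.2.15, so that one stated period applies to these products. The choice of period is for the investigators.

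The cost is a short amendment, a revised eligibility checklist and one added question at existing contacts. The downside is that a few supplement users must stop for the period or are not enrolled. No change to study dosing, sample size or the stopping boundaries is needed.

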7.4.1 Criteria for discontinuation of treatment ("off-treatment")

Patients may withdraw from treatment or the study overall at any time at their own request, or they may be withdrawn at the discretion of the Investigator or Sponsor for safety, behavioral reasons, or the inability of the patient to comply with the protocol-required schedule of study visits or procedures. In addition to the drug-specific discontinuation criteria listed in Dose Modification Section, the following will result in treatment discontinuation:

Version Date: 11APR2023

- Unacceptable Toxicity
- Subject requests to discontinue the study treatment and/or study procedures.
- Non-compliance as defined as missing ≥ 30% of the required Q-Urol/placebo doses. At the discretion of the principal investigator, the subject may be permitted to continue on treatment after the first noted occurrence of non-compliance if the subject is re-educated on treatment administration and compliance can be achieved within a reasonable timeframe.
- Significant protocol violation
- Study terminated by investigator sponsor
- Lost to follow-up

7.4.2 Criteria for discontinuation of study ("off study")

Subjects will be taken off study for the following:

- Completed study end of treatment visit.
- Screen failure.
- The subject is lost to follow-up.
- If, in the investigator's opinion, the continuation of the trial would be harmful to the subject's well-being.
- Development of intercurrent illness or situation which would, in the judgment of the investigator, significantly affect assessments of clinical status and trial endpoints.
- Participant requests to be withdrawn from the study
- Death

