8.1 Dose Modifications

While dose reductions are not permitted on trial, dose interruptions for study treatment-related AEs are allowed as deemed necessary by the treating physician. Doses of Q-Urol/Placebo that were not administered due to toxicity will not be replaced. If a toxicity-

Version Date: 11APR2023

related dose delay extends over 12 days, treatment will be discontinued permanently and the patient should be removed from the study.

Study therapy may be held for any treatment-related adverse events, grade ≥ 2 as deemed necessary by the treating investigator. Upon resolution of the treatment-related adverse event, study therapy may be resumed at the prior dose level and frequency.

If a subject on study therapy experiences a grade \geq 3 SAE attributed to study drug, study therapy will be discontinued.

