10.3 End of Treatment

An End of Treatment visit will occur six weeks after brachytherapy. At this visit, the patient will discontinue Q-Urol, return any remaining medication, the pain medication diary, and the dosing diary for medication reconciliation. For End of Treatment procedures the Schedule of Events and the Assessments Section.

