11.5 Questionnaire administration

All questionnaires will be completed in the clinic by the patient prior to starting study therapy and after completing six weeks of daily Q-Urol/Placebo therapy.

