12.3.2 Evaluable for response

A modified intent-to-treat data set will be used to assess efficacy. Subjects who have successfully undergone brachytherapy and received one dose of Q-Urol will be evaluable for response. Subjects who fail to undergo brachytherapy or begin Q-Urol therapy will be replaced. Those who do not complete the end of treatment patient questionnaires will be considered treatment failures.

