13.2.2 Primary endpoint

There are two planned analyses of the primary endpoint variable: an interim analysis at N1 = 21 patients per group and a final analysis at N = 70 patients per group. Two sample *t*- statistics will be calculated and evaluated as described in 13.2.1.

Multiple imputation will be used to replace missing end of treatment values of the National Institutes of Health-Chronic Prostatitis Symptom Index (NIH-CPSI) total score. A sensitivity analysis will replace missing values by the largest (i.e. worst) observed value.

In addition to formal testing for a difference between groups, the mean change between groups and the mean change within each group together will be reported together with 95% confidence intervals.

Version Date: 11APR2023

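### Sections 7.4.2 and 8.1 take dosed men off study for reasons plausibly tied to outcome or tolerability, and no Day 43 NIH-CPSI is planned after such an exit

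*Combined protocol and SAP*

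**What the plan says.** Two rules take men who have started study drug out of the study itself, not only off treatment.

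- Section 7.4.2 lists, as a reason separate from harm to the patient, "Development of intercurrent illness or situation which would, in the judgment of the investigator, significantly affect assessments of clinical status and trial endpoints". The investigator who judges this is blinded (section 4.2).
- Section 8.1 says that after a toxicity-related dose delay of more than 12 days "treatment will be discontinued permanently and the patient should be removed from the study". The same section only stops therapy for a grade 3 or higher SAE attributed to study drug.

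Table 1 schedules the NIH-CPSI at screening and at the end-of-treatment visit, with nothing between them and no early-termination visit. Section 10.3 dates that visit from the implant: "An End of Treatment visit will occur six weeks after brachytherapy". Section 11.5 instead places the second form "after completing six weeks of daily Q-Urol/Placebo therapy". The only contact planned after the last dose is a call about adverse events.

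These men stay in the efficacy analysis under section 12.3.2: "Subjects who have successfully undergone brachytherapy and received one dose of Q-Urol will be evaluable for response". I read this as study product in either arm. Only men who had no brachytherapy or never started study drug are replaced.

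Three rules cover the missing score:

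- section 12.3.2: "Those who do not complete the end of treatment patient questionnaires will be considered treatment failures";
- section 13.2.2, primary analysis: "Multiple imputation will be used to replace missing end of treatment values";
- section 13.2.2: "A sensitivity analysis will replace missing values by the largest (i.e. worst) observed value".

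**The concern.** The section 7.4.2 rule selects men by the expected effect of an event on the endpoint. The section 8.1 rule selects them by tolerability. In both cases the man may be alive, reachable and willing to fill in a form at a visit already scheduled, yet no section asks him to. His primary value is then missing under the plan's own rules, for a reason that may be related to what the value would have been.

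Multiple imputation fills the gap from men who stayed. Section 13.2.2 gives no imputation model, and there is no on-treatment NIH-CPSI to draw on. If removed men differ from retained men with the same observed data, imputation carries the gap forward. The treatment-failure rule has no numeric meaning in a comparison of means. The worst-value analysis bounds the problem but does not recover the score.

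At stake are bias in the primary difference if removal differs by arm, and an unstated target. Setting aside illness-affected scores is a legitimate aim, but the plan does not state it. Collecting the score would still allow it.

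**Working it through.** **1. Reproduce the design (section 13.2.1).** Inputs: 21 then 70 per arm; futility at t < -1.16; efficacy at t > 2.85; final success at t > 1.67; true difference 0.5 SD. Simulating 200,000 data sets under each hypothesis gives type I error 0.050 (stated 0.05), power 90.1% (stated 90%), futility stop 12.5% under the null (stated 12%), futility stop 0.3% and efficacy stop 12.4% under the alternative (stated 0.3% and 12%). The stated figures hold when all 70 per arm have a score.

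**2. Model for removal (all rates assumed).** In each arm the SD is 1, and a share p is removed whose mean is s SD above (worse than) the arm mean.

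- Mean of retained men = arm mean - s × p/(1-p).
- Difference among retained men = 0.5 - s × [pC/(1-pC) - pT/(1-pT)], with C placebo and T Q-Urol.
- Variance among retained men = 1 - s² × p/(1-p), taking equal spread within the retained and removed groups.

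Examples:
- 5% v 2.5%, s = 1: 0.5 - (0.0526 - 0.0256) = 0.473.
- 10% v 5%, s = 2: 0.5 - 2 × (0.1111 - 0.0526) = 0.383.

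**3. True difference 0.5 SD, same two-stage design, 60,000 trials per cell** (s = 1 / 1.5 / 2):

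| Removed, placebo v Q-Urol | Estimate, retained men | Power, retained men | Power, same loss at random | Power, worst value | Power, Day 43 score collected |
|---|---|---|---|---|---|
| 5% v 2.5% | 0.474 / 0.459 / 0.446 | 0.873 / 0.867 / 0.875 | 0.893 / 0.890 / 0.891 | 0.884 / 0.880 / 0.885 | 0.90 |
| 10% v 5% | 0.441 / 0.413 / 0.384 | 0.830 / 0.822 / 0.836 | 0.878 / 0.880 / 0.883 | 0.871 / 0.866 / 0.879 | 0.90 |
| 5% v 5% | 0.500 in each | 0.90 / 0.92 / 0.94 | not run | 0.806 / 0.828 / 0.861 | 0.90 |

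In the first row about 1 point of lost power is sample size and about 2 points informative missingness. In the second row the informative part is about 5-6 points (for example 0.880 - 0.822 = 0.058). In the third row there is no bias, and leaving the scores out raises power because high scores are set aside: at s = 2 the retained variance is 1 - 4 × 0.0526 = 0.79.

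**4. Does multiple imputation repair it?** I used 20 imputations by regression on arm and baseline, with an assumed baseline correlation of 0.4 and 6,000 trials per cell (s = 1 / 2).

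- 5% v 2.5%: estimate 0.473 / 0.448, power 0.876 / 0.879.
- 10% v 5%: estimate 0.441 / 0.383, power 0.834 / 0.848.

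Under this model the bias stays.

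**5. More men removed on Q-Urol, no benefit.** Type I error depends on which null is meant.

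- *Retained men alike; Q-Urol only adds events* (placebo 2.5% v Q-Urol 5%, up to 5% v 10%; s = 1-2). Rejection is 0.049-0.051. A true worsening of 0.027-0.117 SD among all dosed men is estimated as zero. The worst-value analysis does show a worsening, of 0.06-0.125 SD.
- *Means of all dosed men equal; Q-Urol loses more of its worse men* (10% v 5% placebo, s = 0.5-1). The spurious benefit is s × (0.1111 - 0.0526) = 0.03-0.06 SD, and one-sided type I error is about 0.07-0.10.

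**The case against.** The strongest reply is that the harm needs unequal removal, and nothing in the documents supplies a rate, a ratio or a direction.

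- **Tolerability.** Section 2.2 calls side effects of quercetin rare, and section 3.1.2 reports two mild events among 15 treated men. A hold of more than 12 days in a six-week course would be uncommon. At 3% v 1.5% removed (s = 1-2) the bias is 0.02-0.03 SD and power 0.884-0.887, against 0.892-0.897 for the same loss at random.
- **Direction.** An illness or its treatment could also lower the score, for example through steroids or analgesics.
- **Balanced removal.** Here the present rule is unbiased and at least as powerful as collecting every score.
- **Imputation.** A model using the pain diary, weekly calls and concomitant medications recorded before exit might do better than the one tested.
- **Safeguards.** Removal is decided blind, removed men stay in the efficacy set, and a worst-value analysis is prespecified.

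All of this stands and limits the size of the point. It does not supply a reason to leave the score uncollected. The worst-value analysis is no substitute either: at equal 5% removal its power is 0.81-0.86.

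A reader might infer that any man who stops drug loses his Day 43 form, or that the plan forbids it. The documents do not support that. Section 10.3 times the visit from brachytherapy, section 7.4.1 separates stopping treatment from leaving the study, and a Day 43 form after exit is unplanned rather than prohibited.

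**Conclusion.** The point holds as a gap in planned outcome collection, worth closing by amendment. Collectable primary scores can be missing for reasons plausibly related to outcome or tolerability, imputation from retained men need not correct this, and the worst-value analysis addresses it only in part.

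Its size and direction cannot be determined from the documents. Under the assumed unequal removal with more men lost on placebo, a 0.5 SD benefit is understated by about 0.03-0.12 SD and power falls from 0.90 to about 0.87-0.82. With equal removal of equally worse men there is no bias.

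A reader might also infer that the exits favour Q-Urol or inflate type I error. That follows only if Q-Urol loses more men and the null is equality of means among all dosed men (about 0.07-0.10 in the cells above). If retained men are alike it stays at about 0.05. Nor would a harmful effect go unseen: adverse events are collected until 30 days after the last dose (or until new cancer treatment is initiated; section 16.4.1), and the DSMC reviews them (section 16.3). Confidence is medium, because every rate is assumed.

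**What to change.** - **Section 7.4.2:** make the intercurrent-illness item a reason to stop study drug only. The harm item stays.
- **Section 8.1:** replace removal from the study after a hold of more than 12 days with permanent discontinuation of study treatment.
- **Section 11.5:** state that every dosed patient who has not withdrawn consent completes the NIH-CPSI and the other questionnaires at Day 43 after brachytherapy, whether or not therapy was completed. Include men stopped under the harm item where it is safe to ask them, so that the two sections do not conflict. This also covers the discretionary exits in sections 7.2.3 and 7.4.1.
- **Data:** record the intercurrent event with its date, and any EBRT start date. Section 7.1 already places EBRT after the primary-endpoint evaluations, so the date is a check that an early stopper's score precedes pelvic radiation.
- **Analysis:** keep an analysis that sets aside illness-affected scores as a sensitivity analysis.

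The cost is amendment wording for a visit and forms already scheduled. The downside is more outcome variance. If removal is balanced at 5%, collecting these scores costs roughly 0-4 points of power compared with leaving them out (0.90 against 0.90-0.94).
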